## Introduction

### Background

Primary knee arthroplasty is a frequently performed procedure and is expected to increase in numbers over the next decade [1, 2]. Advantages of unicompartmental knee arthroplasty (UKA) compared to total knee arthroplasty (TKA) include shorter hospital stays, faster recovery [3-6], fewer infections and readmissions [6-9], and lower costs [9]. The length of hospital stay after UKA is variable, but an increased length of hospitalization has been associated with more complications and higher readmission rates [10]. A recent study has shown that the main reasons for continued hospitalization beyond 24 hours after surgery are pain and lack of mobilization [11]. Strategies to decrease the length of stay after UKA should thus be aimed at improved analgesia and postoperative mobilization.

There is a large interindividual variability in the postoperative pain response. It is well documented in TKA-surgery that high pain responders (HPR), evaluated using the Pain Catastrophizing Scale (PCS), have higher postoperative pain responses compared to low pain responders (LPR) [12-15]. Recently, it has been shown that HPR patients undergoing TKA benefit from a larger preoperative dose of glucocorticoid compared to a previously recommended dose [16]. Interestingly, the same difference has not been found in LPR patients (Nielsen et al.: IN PREPARATION, clinicaltrials.gov ID NCT03758170, EudraCT 2018-002634-20, VEK H-18034756). These HPR patients constitute a vulnerable high-risk patient group and potentially benefit from targeted treatment [17].

Currently, the distribution of HPR- and LPR patients and their association with acute pain following UKA is not well investigated. The generated knowledge from this research project is essential to determine how studies with analgesia interventions should be designed. In the future, this will contribute to targeting treatment for high-risk patient groups to reduce pain and improve postoperative mobilization, and ultimately decrease the length of hospital stay in patients undergoing UKA. By targeting treatment, potential overtreatment is also avoided.

### Aim

To investigate the prevalence of high- and low-pain responders, defined by a PCS score  $> 20$  and  $\leq 20$  respectively, as well as the acute postoperative course of pain for these groups after unicompartmental knee arthroplasty.

### Study design

Prospective observational single-center cohort study.

### Sample size

120 patients

### Outcomes

#### Primary outcome

- Ratio between HPR:LPR patients defined as patients with PCS  $> 20$  and PCS  $\leq 20$  respectively

#### Secondary outcomes

- Incidence of moderate to severe pain (VAS  $> 30$  mm) during a 5-meter walk test 24h postoperatively in LPR patients
- Incidence of moderate to severe pain (VAS  $> 30$  mm) during a 5-meter walk test 24h postoperatively in HPR patients

- Differences between HPR- and LPR patients for the following variables:
  - Incidence of moderate to severe pain (VAS > 30 mm) during a 5-meter walk test 24h postoperatively
  - Incidence of moderate to severe pain (VAS > 30 mm) at rest 24h postoperatively
  - Cumulated pain upon ambulation in a 5-meter walk test day 2-7
  - Cumulative use of rescue-analgesics per day in hospital day 0 to discharge, and at home from day of discharge to day 7
  - Quality of sleep, lethargy, dizziness, and nausea pre- and postoperatively from day 0 to day 7
  - Length of stay (LOS) in hospital

#### Inclusion criteria

- Primary unilateral UKA
- Age  $\geq$  18 years
- Ability to participate in the study (understand written and spoken Danish language, self-reported pain, and satisfaction)
- Filled out the Pain Catastrophizing Scale preoperatively
- Signed written informed consent form

#### Exclusion criteria

- Mental disability that could impair a patient's decision-making capability of giving informed consent and not enabling valid data collection
- Insulin-treated diabetes mellitus
- Patients with known diagnoses of schizophrenia, ongoing psychosis, bipolar disease and/or a history of ongoing anti-psychotic treatment
- Patients with modulated pain-reception (experience) based on other diseases or injuries, e.g. spinal cord or brain injury, severe polyneuropathies, or neurologic disorder
- Peripheral nerve block per- or postoperatively

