#### Study plan

In the outpatient clinic, the screening procedure will be performed among patients planned to UKA by the surgeons. Patients will be asked if they may be contacted with the purpose of participating in a research project. Patients will undergo a preliminary examination where, as a standard procedure, the patient will receive a PCS questionnaire. Patients will be informed of the research project either in the outpatient clinic or by phone from an investigator.

All patients will receive verbal and written information about the project. All patients must give a signed informed consent on paper prior to inclusion to participate in the study.

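### As written, the nerve-block exclusion also removes already classified patients from the primary HPR:LPR ratio, which needs only the preoperative PCS (minor)

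*Combined protocol and SAP*

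**What the plan says.** The Exclusion criteria section lists five items. Four are patient characteristics that can be known at screening. The fifth is "Peripheral nerve block per- or postoperatively", which can be known for certain only during or after the operation.

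By that time the patient is already in the study and classified:

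- Inclusion criteria: "Filled out the Pain Catastrophizing Scale preoperatively".
- Study plan: "All patients must give a signed informed consent on paper prior to inclusion to participate in the study".
- Collected variables: rest and walking pain are also recorded preoperatively. Together with consent before inclusion, this places inclusion before surgery, although no consent deadline relative to surgery is given.

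The primary outcome is "Ratio between HPR:LPR patients defined as patients with PCS" above 20 against 20 or below. It uses no postoperative data. The secondary outcomes do, for example "Incidence of moderate to severe pain (VAS > 30 mm) at rest 24h postoperatively".

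The Data analysis section defines no analysis sets. The Sample size and Power calculation sections give 120 patients without saying whether patients excluded for a block are counted or replaced.

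**The concern.** A block alters pain and analgesic use, so the exclusion has a clear purpose for those outcomes. That purpose does not carry over to the PCS ratio, because a block given during or after surgery cannot change a questionnaire score obtained before it.

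Applied to the whole study, the criterion makes membership of the primary denominator depend on a later event. If that event is more common in one PCS group, the ratio is distorted. The Background section reports more postoperative pain in HPR than in LPR patients, on TKA evidence. If blocks are given for pain and the same contrast holds after UKA, HPR patients would be lost more often and their share understated.

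The ratio is the study's main result, and the Background section gives it a practical use: "The generated knowledge from this research project is essential to determine how studies with analgesia interventions should be designed". Someone planning such a study knows the PCS at screening but not who will later receive a block, so the ratio before any block exclusion is the one they need.

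**Working it through.** **The plan's own figure.** The only relevant figure is 120 patients. It cannot be reproduced, because the Power calculation section gives no rate, effect size or precision target and says that a power calculation would be too uncertain. The point does not depend on how 120 was chosen.

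**Inputs.** n = 120 and the two-sided 95% interval come from the plan. The true HPR share s and the block rates bH (HPR) and bL (LPR) are not in the documents; every value below is an assumption.

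**Formulas.** If block recipients are dropped:

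- observed ratio = true ratio × (1 − bH)/(1 − bL)
- observed HPR share = s(1 − bH) / [s(1 − bH) + (1 − s)(1 − bL)]

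**One case in full.** Take s = 0.25, bH = 0.10, bL = 0.03. HPR remaining: 0.25 × 0.90 = 0.225. LPR remaining: 0.75 × 0.97 = 0.7275. Share: 0.225/0.9525 = 23.6%. Ratio: 0.225/0.7275 = 0.309, against a true 0.333.

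**Range.**

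| True HPR share | Block rates HPR/LPR | Ratio multiplied by | Observed share | Shift (points) |
|---|---|---|---|---|
| 25% | 5%/5% | 1.000 | 25.0% | 0 |
| 25% | 3%/2% | 0.990 | 24.8% | −0.2 |
| 25% | 10%/3% | 0.928 | 23.6% | −1.4 |
| 40% | 10%/3% | 0.928 | 38.2% | −1.8 |
| 30% | 10%/5% | 0.947 | 28.9% | −1.1 |
| 20% | 20%/5% | 0.842 | 17.4% | −2.6 |
| 30% | 20%/5% | 0.842 | 26.5% | −3.5 |
| 40% | 20%/5% | 0.842 | 36.0% | −4.0 |

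**Sampling error for comparison.** Wilson 95% intervals at n = 120:

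| HPR share | Interval | Half-width (points) |
|---|---|---|
| 20% | 13.8% to 28.0% | 7.1 |
| 25% | 18.1% to 33.4% | 7.7 |
| 30% | 22.5% to 38.7% | 8.1 |
| 40% | 31.7% to 48.9% | 8.6 |

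Every shift in the range is smaller than the matching half-width. The interval covers sampling error only and would not reflect this shift.

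**Denominator.** Equal rates leave the ratio unbiased but still cost patients: 5%/5% leaves 114 of 120. At 20%/5% with a 30% HPR share, about 109 remain (108.6).

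**With the exclusion kept out of the primary outcome,** the multiplier is 1 and all 120 included patients count.

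**The case against.** The strongest reply is that the Aim section sets one aim for one cohort: the prevalence of the two groups, "as well as the acute postoperative course of pain for these groups after unicompartmental knee arthroplasty". On that view a single denominator for prevalence and pain is a legitimate choice, and splitting it gives something up. This stands as a cost, but a small one: at 10%/3% with 30 HPR and 90 LPR patients, 30 × 0.10 + 90 × 0.03 = 5.7, so about 6 of 120 would count in the ratio but not in the pain outcomes.

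The line may also be meant for a planned anaesthetic technique. The text does not say so, and a block given postoperatively naturally includes an unplanned one. If that is the meaning, one clause settles it.

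A reader might infer that the plan contains a built-in systematic error that understates the HPR share. The documents do not support that. They give no block rate, no reason for blocks and no difference by PCS group. The pain-driven mechanism fits postoperative blocks; an intraoperative block precedes any postoperative pain score, and nothing links it to the PCS. The HPR/LPR pain contrast comes from TKA, and the Power calculation section expects pain to be higher there, while noting that this is not known.

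A reader might also want to add a 24 h pain analysis that counts rescue blocks as VAS > 30 mm, expecting it and the exclusion analysis to bracket the incidence without blocks. They need not. Suppose that incidence is 60%, with 5% intraoperative and 5% rescue blocks, and all recipients would have exceeded 30 mm. Exclusion gives (0.60 − 0.10)/0.90 = 55.6%. Counting only the rescue blocks gives (0.60 − 0.05)/0.95 = 57.9%. Both lie below 60%, so that analysis is not proposed.

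**Conclusion.** The point holds as a minor one. Followed literally, the criterion takes classified patients out of a primary outcome that needs only their preoperative PCS, because of something that happens later. This is a stated rule with that effect, and so more than a missing detail.

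Bias in the ratio is possible but not shown. It is zero when block rates are equal, and it runs towards understating HPR only if HPR patients receive more blocks. Under assumed rates from 3%/2% to 20%/5% and assumed HPR shares of 20% to 40%, the share falls by about 0.2 to 4 points, within sampling error at n = 120. That the shift is small is itself conditional on those rates, since the documents anchor none of them. The study describes itself as descriptive and hypothesis-generating, and its conclusions are not threatened by this.

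**What to change.** Add to the Exclusion criteria or Data analysis section:

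1. The primary HPR:LPR ratio is computed on all included patients with a preoperative PCS, regardless of any later block.
2. The block exclusion applies only to the postoperative pain and analgesic outcomes.
3. A statement of whether the 120 is counted before or after block exclusions.
4. Block recipients are reported by HPR/LPR and by timing (intra- or postoperative). The Collected variables section already lists participant numbers, perioperative analgesics, type and dose of analgesia from day 0 to day 7, and deviations from standard treatment, which should largely suffice.

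If the criterion covers only blocks planned before inclusion, say that instead.

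The cost is a few sentences, with no extra patients or procedures. The downside is slightly different denominators for the primary and pain outcomes. Clinical use of blocks is unaffected.

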### Collected variables

During the hospital stay, data will be collected by contacting the patient at the Orthopaedic Dept. and by accessing the electronic patient journal. After discharge patients will be asked to fill out an electronic pain diary until 7 days after the operation. The following variables will be collected:

- Number of participating patients (CONSORT)
- Pain during rest (VAS 0-100 mm), measured preoperatively, 24 h postoperatively, and twice a day from day 2 to 7
- Pain upon ambulation in a 5-meter walk test (VAS 0-100 mm), measured preoperatively, 24 h postoperatively, and twice a day from day 2 to 7
- Quality of sleep, lethargy, dizziness, and nausea pre- and postoperatively from day 0 to day 7.
- PCS score
- Preoperative analgesia
- Use of rescue-analgesia from day 0 to day 7
- Type and dose of analgesia from day 0 to day 7
- Length of stay (LOS) in hospital, and reasons for prolonged stay (>2 postoperative days)
- Demographical data (gender, age, height, weight, co-morbidity, American Society of Anesthesiologist (ASA) score).
- Surgical data (date of surgery, indication, surgical time, procedure information, intraoperative bleeding, transfusion data, perioperative analgesics)
- Deviations from standard treatment

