## Statistics

### Power calculation

There is no relevant acute pain data from UKA patients, thus, sample size estimates are based on data from TKA patients. The pain response is expected to be higher in a TKA population, although this is not known. However, the relative difference in pain between HPR- and LPR-patients is not necessarily different in UKA patients. We are not familiar with the ratio between HPR- and LPR-patients based on PCS score in UKA, and thus a power calculation will be associated with substantial uncertainty. For this reason and because of the descriptive hypothesis-generating nature of the study, we will include 120 patients.

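### The nerve-block exclusion acts after PCS classification, so the primary HPR:LPR ratio depends on a later event; the effect is probably small and cheap to remove

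*Combined protocol and SAP*

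**What the plan says.** All references are to the combined protocol and SAP.

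- Exclusion criteria: the last item is "Peripheral nerve block per- or postoperatively", that is, a block during or after surgery. The other four items describe conditions that can be known before surgery.
- Inclusion criteria: "Filled out the Pain Catastrophizing Scale preoperatively". Study plan: "Patients will undergo a preliminary examination where, as a standard procedure, the patient will receive a PCS questionnaire".
- Study plan: "All patients must give a signed informed consent on paper prior to inclusion to participate in the study". Under Collected variables, study pain is first scored before surgery, so enrolment precedes the operation.
- Primary outcome: "Ratio between HPR:LPR patients defined as patients with PCS" above 20 and at or below 20. Nothing but the PCS score enters the definition.
- Secondary outcomes: 24 h pain incidences within and between the groups, cumulated walking pain, "Cumulative use of rescue-analgesics per day in hospital day 0 to discharge" (continued at home to day 7), and length of stay (LOS).
- Collected variables: type and dose of analgesia, and "Deviations from standard treatment".

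No section defines an analysis population, says whether blocked patients are replaced, or keeps them in any analysis. None gives the frequency, timing or reason of blocks.

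**The concern.** The Aim has two parts: the prevalence of HPR and LPR patients, and their acute pain course. The criterion touches both, in different ways.

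The prevalence needs only a preoperative score. Dropping a classified patient because of a later block cannot make that score more valid, but it changes the ratio whenever block rates differ between the groups.

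For the pain course, the question is why a block is given. A block planned as part of the anaesthetic does not select on postoperative pain. A block given afterwards because the patient hurts does: the patients removed are those with the outcome being described. The Background cites evidence from total knee arthroplasty that HPR patients have more postoperative pain, so more blocks in that group would be plausible, though this is not established for the unicompartmental operation. The results are meant to guide the design of analgesia studies, so the within-group incidences matter as well as the difference.

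**Working it through.** **Inputs.** The protocol sets the sample size at 120 without a power or precision calculation, so there is no figure to reproduce. It says that the HPR share in this population is not known. HPR shares, block rates and pain incidences below are therefore assumptions.

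**1. Primary ratio.** Let p be the true HPR share. After exclusion:

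- HPR share = p(1 − bH) / [p(1 − bH) + (1 − p)(1 − bL)]
- HPR:LPR ratio = true ratio × (1 − bH)/(1 − bL)
- 95% half-width = 1.96 × √(p(1 − p)/120)

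| p | bH | bL | Share after exclusion | Shift (points) | Half-width (points) |
|---|---|---|---|---|---|
| 20% | 10% | 2% | 18.7% | −1.3 | 7.2 |
| 30% | 10% | 2% | 28.2% | −1.8 | 8.2 |
| 40% | 10% | 2% | 38.0% | −2.0 | 8.8 |
| 30% | 4/36 | 2/84 | 32/114 = 28.1% | −1.9 | 8.2 |
| 30% | 20% | 5% | 26.5% | −3.5 | 8.2 |
| 30% | 2% | 10% | 31.8% | +1.8 | 8.2 |
| 30% | 2% | 2% | 30.0% | 0 | 8.2 |

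In the fourth row the ratio goes from 36:84 (1:2.33) to 32:82 (1:2.56). The shift formula does not contain the sample size, so replacing excluded patients at the same block rates would not remove the shift. Counting every classified patient makes it exactly zero at any block rates.

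**2. Walking pain at 24 h.** Assume that without blocks 22/36 HPR (61.1%) and 42/84 LPR (50.0%) have VAS > 30 mm, a difference of 11.1 points. The half-width for that difference is 1.96 × √(0.611 × 0.389/36 + 0.25/84) = 19.2 points.

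- Blocks for pain in 4 of these HPR and 2 of these LPR patients, all excluded: 18/32 − 40/82 = 56.3% − 48.8% = 7.5 points.
- Blocks in 3 HPR and 6 LPR patients instead, all excluded: 19/33 − 36/78 = 57.6% − 46.2% = 11.4 points. The difference hardly moves, but both incidences fall.

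**3. Ways of handling the six blocked patients (4 HPR, 2 LPR).** Let f be the share of blocks still holding VAS at or below 30 mm at 24 h, equal in both groups.

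- Retained, VAS as measured: difference = 11.11 − (4/36 − 2/84) × 100 × f = 11.11 − 8.73f. This is 2.4 at f = 1, 6.7 at f = 0.5 and 11.1 at f = 0.
- Excluded: 7.5. Measured VAS is further than this from 11.1 once f exceeds (11.11 − 7.47)/8.73 = 0.42.
- Block for pain counted as moderate to severe pain: 11.1. This holds by construction, because every blocked patient was assumed to have VAS > 30 mm, so it is not evidence for that option.

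**The case against.** The strongest objection is that the effect rests on stacked assumptions. Nothing in the protocol says that rescue blocks are used in this unit, and the example in the fourth table row needs blocks about 4.7 times as often in HPR as in LPR patients (11.1% against 2.4%). The study is presented as having a "descriptive hypothesis-generating nature of the study", and every shift shown lies inside sampling error. Analgesia and deviations from standard treatment are collected, so blocks could be disclosed. This stands, and it keeps the point minor. It does not remove the point: a confidence interval does not allow for selection, and no section requires blocks to be reported by PCS group.

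A second objection is that pain without a regional block is a coherent target, and that one population keeps the prevalence and the pain course on the same patients. That is a fair reason for the intraoperative exclusion in the postoperative outcomes. It is a weak reason for conditioning a preoperative prevalence on a later event.

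A reader might infer that rewording the criterion cures everything, or that blocked patients should simply stay in with their recorded VAS. Neither follows. Rewording removes the problem only for the ratio. For pain, a working block lowers VAS, and the documents say nothing about block duration that would show measured VAS to be better than exclusion.

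**Conclusion.** The timing follows from the text: the criterion acts on patients already consented and classified. No section says expressly that blocked patients leave the ratio, but that is the plain reading of an exclusion criterion.

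Under assumed rates of 10% to 11% against 2%, the HPR share moves by about 2 points, against a half-width of about 8. In the walking-pain illustration the difference moves from 11.1 to 7.5 points, against a half-width of 19.2. The second result also assumes that the blocks are given for pain to patients who would have had VAS > 30 mm.

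A reader might infer that the plan understates the HPR share, or that its results would be unreliable. The documents support neither. Size and direction depend on block rates they do not give: reversed rates raise the share, equal rates leave it unchanged, and without blocks nothing changes. This is a minor point and a cheap improvement.

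**What to change.** 1. Compute the primary ratio in every consented patient who meets the other criteria and has a preoperative PCS score, whatever block is given later.
2. For the postoperative outcomes, limit the exclusion to blocks given during surgery. Keep postoperatively blocked patients in LOS and rescue-analgesic use, with the block reported as a separate count.
3. Report block numbers, timing and reasons by PCS group.
4. For the 24 h pain incidences, keep the analysis without blocked patients. Add a sensitivity analysis that counts a postoperative block given for pain before the assessment as moderate to severe pain. Do not make VAS as measured the main pain analysis.

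The cost is a few sentences, one sensitivity analysis and one descriptive table row, with the time and reason of each block added to the data collected. No care changes and no patients are added. The downside is that the ratio and the pain outcomes may rest on slightly different patient numbers, which the patient-flow account can show.

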#### Study location

The inclusion will take place at the Dept. of Orthopaedic Surgery, Arthroplasty unit at Hvidovre Hospital, Capital Region of Denmark.

#### Timespan

Expected start of project: September 1, 2022

Expected end of data collection: July 1, 2023

Expected end of data analysis: September 1, 2023

#### Study plan

In the outpatient clinic, the screening procedure will be performed among patients planned to UKA by the surgeons. Patients will be asked if they may be contacted with the purpose of participating in a research project. Patients will undergo a preliminary examination where, as a standard procedure, the patient will receive a PCS questionnaire. Patients will be informed of the research project either in the outpatient clinic or by phone from an investigator.

All patients will receive verbal and written information about the project. All patients must give a signed informed consent on paper prior to inclusion to participate in the study.

